9.1 Statistical Analysis

9.1.1. Recruitment and retention: Participant log data will be used to assess recruitment to targets and retention rates. A full-scale trial would be considered feasible if recruitment targets were met and a rate of 75% retention achieved. If retention is below 75% but at least 60%, we will consider whether any identified barriers could be addressed to improve recruitment and/or retention to acceptable levels and hence make a full-scale evaluation trial potentially feasible; in this situation, the success of strategies to overcome these barriers would be expected to be assessed during an internal pilot phase. Questionnaire and interview data will clarify possible barriers to recruitment and retention, in addition to assessing whether the intervention was delivered consistently and according to the clinical protocol, which will be addressed, where possible, in preparation for a definitive trial.

9.1.2. Acceptabilty of a participation, usual care and the intervention and quality of implementation will be explored through analysis of the intervention log, questionnaires and interviews.

Thematic analysis conducted in six recursive phases (Braun and Clarke 2006), using multiple analysts to ensure credibility; will establish participants' views and experiences of recruitment, usual care in the control phase (Phase 1), components of the intervention including psychosocial support, preparation for birth and psychological measures used. Data will also help determine appropriateness of proposed outcomes measures. Participants' views and experiences of completing questionnaires and attending interviews will contribute to evaluating the burden of trial assessments and inform data collection methods for the main trial. The views and experiences of healthcare staff delivering the intervention and others involved in care will be used to determine acceptability of the intervention and fidelity of the components as delivered in practice compared with those planned, including any impacts on wider services. This data will also identify any areas where further refinement of the intervention is needed.

9.1.3. Psychological assessments, and clinical data: Quantitative data will be inputted into an electronic system (REDCap). REDCap (Research Electronic Data Capture) is a secure web application used to build and manage the on-line Case Report Form (https://www.project-redcap.org/). The University of Manchester is a member of the REDCap Consortium. Outcome measures will be compared descriptively, using frequencies and percentages for categorical variables and descriptive statistics including means, standard deviations, medians and ranges for numerical variables. Data from psychological tools will be compared to determine whether characteristics, including rates of missing items/scale totals are comparable across different measures. Analysis will focus on the estimation of confidence intervals for differences between the control and intervention cohorts and the estimation of variances to inform the design of the full scale trial.

9.2 Sample Size:

A formal power calculation is not appropriate for a feasibility study, therefore an approximate sample size of 50 women and 30 healthcare workers has been determined pragmatically according to the accepted criteria for feasibility studies (Whitehead et al.)

2016). These numbers will allow implementation of the intervention in the study site and estimation of recruitment/ retention rates and uptake.

10) DATA MONITORING AND QUALITY ASSURANCE

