5.1 Methodology and methods

A mixed methods approach will be used throughout this hospital-based feasibility study designed in accordance with MRC framework for Developing and evaluating complex interventions (MRC 2008). The pragmatic paradigm, which has gained increasing popularity amongst healthcare researchers in recent years, will inform research design for this study. This approach, often termed the 'third way' emerged in response to the inherent limitations of traditional paradigms, including post-positivism and constructivism, in fully addressing multifaceted research questions (Tashakkaori and Teddlie 1998). The pragmatic approach has intuitive appeal for health-care research as rigid adherence to any particular

philosophical stance is rejected and the emphasis is placed on the research question and how best to address it (Armitage 2007). Methods of data collection and analysis are selected according to the likelihood of providing insight into the question (Creswell 2003). Pragmatism underpins the use of mixed methods research, accepting qualitative and quantitative methods either in parallel or sequential stages (Tashakkaori and Teddlie 1998, Creswell 2003). Advocates of mixed-methods research argue that this integration of approaches enhances the quality of many studies, increasing the breadth and depth of enquiry into complex social phenomena (Tashakkaori and Teddlie 1998).

For a full-scale evaluation, individual randomisation would be undesirable due to the risk of contamination between the trial arms and the organisational-level changes required by the intervention. A stepped-wedge (one-way crossover) design in which the intervention is rolled out in phases, the order determined at random but all clusters receiving the intervention by the end of the trial, is currently considered as the most appropriate design. For feasibility, a pre and post-cohort design, over 12 months, will be conducted to allow implementation of the intervention in the study site and assessment of the feasibility of a stepped wedge approach.

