5.2 Setting

The study will take place in a health facility in the metropolitan province of Bulawayo in Zimbabwe. MPilo Central Hospital is the largest hospital in Bulawayo, and second largest in Zimbabwe after Parirenyatwa Hospital in Harare. Mpilo is a public hospital and referral centre for the Matabeleland North, Matabeleland South and Midlands provinces of Zimbabwe. Births per year exceed 9,000. The hospital is a teaching hospital for obstetric care providers and centres for research and specialised care. Data from our recently performed cross-sectional study (UREC Ref 2018-4429-6165), confirms women in a subsequent pregnancy following stillbirth book for antenatal care between 18-35 weeks gestation (median 26 weeks).

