Individual consent will not be sought for attendance at either the current antenatal clinic (control phase 1) or the proposed specialised antenatal clinic (intervention phase 2), as both are considered standard practice. The current antenatal clinic running throughout Phase 1 will be superseded with the specialised antenatal clinic in Phase 2 of the study period. Both will be provided for all women attending antenatal services at the study site who have experienced a previous stillbirth, irrespective of their participation in the study / questionnaire completion / focus group / individual interview participation.

Consent will be sought for data collection associated with the assessment of the feasibility of a full-scale trial, acceptability and uptake of the intervention for women and facility staff. Identification of women with a history of stillbirth will be undertaken by appropriately trained and experienced members of the clinical team and confirmation of eligibility and consenting of participants undertaken by research assistants/midwives.

6.3.1. Women:

Eligible women will be initially identified and approached via a member of the clinical care team at the woman's hospital booking appointment who will introduce the study. If

permission to consider the study has been granted, they will notify the research assistant/midwife to discuss the study further. Written and verbal information (available in local languages) will be supplied and potential participants will be given time to consider participation. The woman will be encouraged to discuss with family/others (if accompanying her) and provided additional opportunities to ask questions. She will be informed that her participation is voluntary and a decision not to take part in the research will have no impact on her current or future healthcare provision. Women will be given the opportunity to confirm participation at the booking visit should they wish and provided with the consent form to sign. Others will be given the opportunity to confirm participation at their next antenatal clinic appointment, where consent form completion will take place. Women will be able to withdraw up until 1 week after taking part in the interviews.

6.3.2. Health workers (midwives, nurses, obstetricians, and support staff) and other hospital staff, including managers and administrators:

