8.4. Psychological assessments

Women participants will complete the psychological assessment questionnaires at the time of booking and towards the end of their pregnancy:

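### Section 9.1.3 names no use of the booking score in comparing two small non-randomised cohorts, and sections 8.4 and 6.3.1 conflict on when that score is taken

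*Protocol*

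**What the plan says.** The design in Protocol section 5.1 is non-randomised and at one site: "a pre and post-cohort design, over 12 months, will be conducted". For the psychological and clinical data, section 9.1.3 states that "Outcome measures will be compared descriptively, using frequencies and percentages for categorical variables", with means, standard deviations, medians and ranges for numerical variables. It adds that "Analysis will focus on the estimation of confidence intervals for differences between the control and intervention cohorts", together with "the estimation of variances to inform the design of the full scale trial". No model, covariate or baseline term is named.

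Section 8.4 provides a baseline for the same scales: "Women participants will complete the psychological assessment questionnaires at the time of booking and towards the end of their pregnancy". Section 6.3.1 allows consent at the booking visit but continues: "Others will be given the opportunity to confirm participation at their next antenatal clinic appointment, where consent form completion will take place". Section 6.3 says that the specialised clinic replaces the current one in Phase 2 and serves every woman with a previous stillbirth, whether or not she joins the study. Section 5.2 reports that these women book between 18 and 35 weeks, with a median of 26.

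**The concern.** The two cohorts are recruited in different months and are small, so their booking scores may differ by chance or because of the period. A raw difference in late-pregnancy scores carries part of any such gap. Booking gestation spans 17 weeks (35 − 18), so the interval between the two questionnaires also varies widely between women.

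The variance output is affected too. Section 4.2.2 makes the full-trial sample size an objective. If that trial used one of these scales and adjusted for its baseline, it would need the residual SD or the booking-to-late correlation as well as the raw SD.

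The timing conflict bears on whether the first score is a baseline at all. A Phase 2 woman who consents at her second visit may already have met the specialised clinic, while her Phase 1 counterpart has had usual care only. The first score would then mean different things in the two cohorts, and adjusting for it could remove part of any effect.

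**Working it through.** **Cohort size.** Section 5.3 gives 25 to 30 eligible women per two-month phase and 25% refusal: 25 × 0.75 = 18.75 and 30 × 0.75 = 22.5. The stated figure of about 20 per phase is reproduced. At the 75% retention criterion of section 9.1.1, 20 × 0.75 = 15 per cohort would have a late score. (Two phases give 37.5 to 45 women, below the 50 in section 9.2. That section calls its figure pragmatic, and nothing here rests on it.)

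**Assumed input.** The correlation r between booking and late scores is not in the Protocol. I use r = 0.3, 0.5 and 0.7, and r = 0 as the unfavourable case.

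**Chance imbalance at booking.** In SD units, the standard error of the booking difference is √(2/n).
- n = 20: √(2/20) = 0.316. P(gap > 0.3 SD) = 2[1 − Φ(0.3/0.316)] = 0.34; P(gap > 0.5 SD) = 0.11.
- n = 15: √(2/15) = 0.365. The same probabilities are 0.41 and 0.17.

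These exclude any systematic difference between periods. A booking gap d carries r × d into the raw late difference. For d = 0.5 SD that is 0.15, 0.25 and 0.35 SD at r = 0.3, 0.5 and 0.7.

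**Interval half-widths (95%, SD units).**
- Raw: t(2n−2) × √(2/n).
- Adjusted for booking score: t(2n−3) × √(2/n) × √(1−r²) × √(1 + 1/(2n−4)). The last factor is the expected cost of chance imbalance.

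| n per cohort | Raw | r = 0 | r = 0.3 | r = 0.5 | r = 0.7 |
|---|---|---|---|---|---|
| 20 | 0.64 | 0.65 | 0.62 | 0.56 | 0.46 |
| 15 | 0.75 | 0.76 | 0.73 | 0.66 | 0.55 |

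At n = 20 the adjusted interval is about 1.5% wider at r = 0, and about 3%, 12% and 27% narrower at r = 0.3, 0.5 and 0.7. At n = 15 the loss at r = 0 is about 2%. If the 50 women of section 9.2 were split evenly, 25 per cohort, the raw half-width would be 0.57.

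**Variance for planning.** Raw variance exceeds residual variance by the factor 1/(1−r²): 1/0.75 = 1.33 at r = 0.5 and 1/0.51 = 1.96 at r = 0.7. Clustering is a separate matter.

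**Timing.** Section 8.4 places the first questionnaire at booking for all women participants. Section 6.3.1 has some of them sign consent only at the following appointment. Both cannot hold for those women. The Protocol does not say how many there would be, or whether the booking visit itself delivers part of the intervention.

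**The case against.** A reader might infer that the Protocol commits to unadjusted differences. It does not: section 9.1.3 names no estimator and does not exclude adjustment, and covariates are commonly left to a statistical analysis plan, which is not shown. A reader might also infer that adjustment is free. It costs one degree of freedom per covariate, drops women without a booking score, gains little at r = 0.3 and loses slightly at r = 0.

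Further, no decision rests on these intervals. Section 7 names recruitment and retention as the key outcomes, section 9.1.1 builds the feasibility criteria on them, and section 9.2 disclaims a power calculation. Section 4.2.2 leaves the full trial's design and outcomes open, so a baseline-adjusted trial on these scales is only a possibility. Adjusting for a score taken after exposure does harm that the raw difference avoids. Some contact data are already planned: healthcare utilisation on the case report form (section 7) and the intervention log (section 8.3.1). The booking range comes from an earlier study at the site and shows spread, not a difference between cohorts.

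All of this stands, and it limits the point to a small one. It does not answer two things. The baseline is collected for every woman, yet the section that sets out the analysis gives it no role. And the conflict over when it is collected lies in the Protocol's own text, where no later analysis plan can supply a score that was not taken.

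**Conclusion.** The point holds as a minor improvement to a secondary analysis. Section 9.1.3 is not in error in planning raw differences and SDs, but it names no use of a booking score that section 8.4 already collects. The gain in precision depends wholly on the assumed correlation: from a loss of about 1.5% at r = 0 to a gain of about 27% at r = 0.7, with 20 women per cohort. Adjustment deals with measured imbalance in the booking score only. It leaves period effects and unmeasured confounding in place, so the adjusted figure should not be read as an estimate of efficacy.

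The contradiction between sections 8.4 and 6.3.1 is definite. Its size is unknown, because the share of women consenting after booking is not given.

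**What to change.** - **Section 9.1.3.** For each late-pregnancy scale, report beside the raw cohort difference one adjusted for booking score and, if numbers allow, booking gestation, each with a 95% confidence interval. State how many women enter each estimate. Report raw SD, residual SD and the booking-to-late correlation.
- **Sections 8.4 and 6.3.1.** Reconcile them by stating when women who consent at a later visit complete the first questionnaire. Record its date, the gestation at that date, and the number of specialised-clinic contacts already made. Giving the questionnaire before that day's appointment would not restore a baseline for women who have already attended once, so flag their scores.
- **Sensitivity analysis.** Repeat the adjusted analysis without first scores taken after specialised-clinic contact.

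The cost is a few lines of text and a few data fields, partly derivable from records already planned. No further questionnaire is asked of the women. In the analysis, each covariate uses one degree of freedom, and women without a booking score drop out of the adjusted estimate only.

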10.1 Trial management

This study will be subject to the audit and monitoring regime of the sponsor, The University of Manchester. Formal monitoring via a data monitoring committee will not be undertaken during this feasibility study as the anticipated risk of harm is low. The existing NIHR Global Health Research Group for Stillbirth Prevention and Management in Sub-Saharan Africa at The University of Manchester Advisory Board chaired by [name] (Liverpool School Hygiene and Tropical Medicine) will provide technical support and advice on the conduct of the feasibility study and full trial. The independent Advisory Board will review the study protocol prior to commencment of the research and any amendments, receive progress updates, advise on issues arising with the study conduct and dissemination of the findings in preparation for a full trial.

The study will be managed by [name] with support from the research team and country principal investigators. A start up meeting with UK and local research teams will be held in-country (Bulawayo, Zimbabwe in Month 1) The Zimbabwe Study leads will be responsible for day to day co-ordination of trial activity from month 1-month 12, supported by research assistants/midwives, Meetings between the CI/UK research team and Country leads will be conducted via Zoom 2 weekly initially and at least monthly for the duration of the research. The wider research team, including all co-applicants and the Africa research leads, research assistants/midwives will meet bi-monthly to review progress and compliance with research governance.

10.3. Safety Reporting: Adverse Event definitions and reporting

For the purposes of this study the following definitions will apply:

10.3.1. Adverse events (AE)

Definition:

Any untoward medical occurrence in a participant recruited to the study, including occurrences which are not necessarily caused by or related to the intervention.

For this study the following is a list of expected maternal and neonatal adverse events which will be recorded but not reported:

Common pregnancy related complications:

Anaemia defined as haemoglobin level <110 g/L at booking, <105 g/L in 2^{nd} and 3^{rd} trimesters, <100 g/L postpartum

Hypertension

New onset/gestational diabetes

Small for gestational age fetus (Estimated fetal weight <10th centile by ultrasound)

Fetal malpresentation

Vaginal bleeding/APH/ placenta praevia identified on ultrasound scan

Premature rupture of membranes

Bacterial or viral infection

Labour related complications including: 3rd or 4th degree perineal tear, postpartum haemorrhage

Common neonatal complications

Jaundice

Feeding problems

Bacterial or viral infections

Psychological instruments

Any other abnormal or concerning findings arising from questionnaires will be reported by the research assistant/midwife to the CI directly and in accordance with the adverse event protocol as above.

10.3.2. Serious adverse events (SAE)

Definition:

Any adverse event (see definition at 10.3.1) that:

- a) results in death,
- b) is life-threatening,
- c) requires hospitalisation or prolongation of existing hospitalisation,
- d) results in persistent or significant disability or incapacity
- e) Or is otherwise considered medically significant by [name] [name] or [name] or [name]. (Health Research Authority, 2015)

The following are expected serious maternal and neonatal adverse events which will be recorded but not reported for further investigation:

Pregnancy related complications:

Admission to hospital for anaemia.

Admission to hospital for hypertension.

Admission to hospital with new onset/ gestational diabetes

Admission to hospital for monitoring or care related to small for gestational age fetus (Estimated fetal weight <10th centile by ultrasound)

Admission to hospital with fetal malpresentation

Admission to hospital with vaginal bleeding/APH/ placenta praevia/premature rupture of membranes (identified clinically, or on ultrasound scan)

Admission to hospital for investigation or treatment of bacterial or viral infection Admission to hospital for elective birth.

Prolongation of admission or readmission related to labour related complications eg

Neonatal complications

Admitted to special care/neonatal unit after birth

Admission to hospital for jaundice

Admission to hospital with feeding problems

Admission to hospital with bacterial or viral infections

10.3.3. Recording and reporting:

AND

Adverse events will be recorded in study documentation by the research co-ordinator, and collated for each participant on an Adverse Event Form at the end of the study. Adverse events will be reviewed at the end of the study by the NIHR Group Advisory Board and the Sponsor.

Serious Adverse Events (other than those listed above) will be recorded on a SAE report form and reported by the research assistant/midwife co-ordinator to the CI as soon as possible after becoming aware (normally within 24 hours).

SAEs will be reported to the to the Sponsor and Research Ethics Committee (REC) if in the opinion of [name] [name], [name], [name] they are:

Related - that is resulted from administration of any research procedures

Unexpected –that is, the type of event is not listed in the protocol as an expected event

A **SAE** meeting these criteria with be reported in writing using the Serious Adverse Event Report as soon as possible and within 15 days of the CI becoming aware of the SAE. SAEs will be reviewed by the Sponsor using their standard criteria and a specific course of action will be recommended for the study and implemented by the Investigators.

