Significantly, associated risk factors vary across the globe, making it important for each country to understand their local causes so that appropriate screening and treatment strategies can be implemented (Goldenberg et al 2009). To this end, we recently carried out a cross-sectional study in Bulawayo, Zimbabwe (UREC Ref 2018-4429-6165). Data were collected by reviewing finished episodes of health records for 1807 women birthing at the study site, Mpilo Central Hospital including 64 stillbirths. Maternal age (OR 1.03, 95% CI 1.00 to 1.07), history of stillbirth (OR 224.8, 95% CI 113.7 to 74.9), ambulance travel (vs non-ambulance travel) (OR 2.10, 95% CI 1.13 to 3.72), reduced fetal movements (OR 109.8, 95% CI 51.03 to 254.0) and 'other' method of birth vs spontaneous vaginal birth (OR 22.72, 95% CI 7.87 to 62.55) all gave an increased odds of stillbirth. Any antenatal care (OR 0.16, 95% CI 0.09 to 0.30), \geq 4 ANC visits (OR 0.19, 95% CI 0.08 to 0.37), syphilis positive (OR 0.36, 95% CI 0.15 to 1.06), tetanus vaccination (OR 0.12, 95% CI 0.06 to 0.28) and gestational age (OR 0.66, 95% 0.60 to 0.71) a decreased odds of stillbirth.

Current recommendations for care in subsequent pregnancies have focused primarily on data from high-income countries (ACOG 2009, Robson et al 2006, Siassakos 2010). Heightened antenatal surveillance has been recommended for women with a previous stillbirth (RCOG 2011, Heazell and Clewlow 2015, Stillbirth Priority Setting Partnership 2015, Silver et al 2018). Priority conditions to address include pregnancy-induced hypertension; antepartum haemorrhage; maternal infections such as syphilis, malaria and HIV; and obstetric risk conditions such as multiple pregnancy and abnormal lie (Lawn et al 2009, Menezes et al 2009, Page and Silver 2017). Women often want increased antepartum surveillance and early birth in these pregnancies (Robson et al 2009) but in many cases the medical benefits of such practices remain uncertain (Wojcieszek et al 2016).

The need for specialist care should also take into account the additional psychological needs of parents during pregnancies that follow a stillbirth (Mills et al 2014, Heazell and Clewlow 2015, Burden et al 2016, Ellis et al 2016, Wojcieszek et al 2016, Shakespeare et al 2018). Notably, subsequent pregnancies are associated with high stress and anxiety for parents

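### The expected-SAE exemption has no severity limit, so a listed admission that becomes life-threatening or disabling gets no SAE form and no 24-hour report to the CI

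*Protocol*

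**What the plan says.** Section 10.3.2 defines a serious adverse event by five alternative criteria. Criterion a is an event that "results in death" and criterion b one that "is life-threatening". Criterion c is hospitalisation or its prolongation, d is lasting or significant disability, and e is medical significance in the judgement of named clinicians.

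The same section then gives a list under the sentence "The following are expected serious maternal and neonatal adverse events which will be recorded but not reported for further investigation". Its entries are admissions, for example "Admission to hospital for hypertension". Others cover vaginal bleeding/APH, investigation or treatment of infection, admission of the baby to special care or the neonatal unit, and neonatal admission with infection.

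Section 10.3.3 builds two reporting routes on that list:

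- **To the CI, normally within 24 hours:** "Serious Adverse Events (other than those listed above) will be recorded on a SAE report form" and passed on to the CI.
- **To the Sponsor and REC, within 15 days of the CI becoming aware:** only SAEs judged both related to research procedures and unexpected, where unexpected means that "the type of event is not listed in the protocol as an expected event".

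Adverse events are otherwise collated per participant, and reviewed by the Advisory Board and the Sponsor, when the study ends (section 10.3.3). Section 10.1 states that there is no data monitoring committee.

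**The concern.** Exempting routine, foreseeable obstetric admissions from expedited reporting is normal practice. Here, though, the exemption is attached to the kind of admission and not to the reason the event is serious. An overnight stay for blood-pressure monitoring and a life-threatening hypertensive emergency both enter as an admission for hypertension. Nothing in the rule separates them.

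The affected conditions are central to this population. The Background (section 3) says: "Priority conditions to address include pregnancy-induced hypertension; antepartum haemorrhage; maternal infections such as syphilis, malaria and HIV". Section 5.4.2 treats the women attending the new clinic as high risk. The Background also says it is not known whether the benefits of closer surveillance outweigh its harms, and that interventions of this kind need monitoring. What is at stake is whether the CI hears of the most severe maternal and neonatal cases while the clinic is running or only after it has finished.

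**Working it through.** No sample size, event rate or test is involved, so there is no figure to reproduce. The check follows the wording of 10.3.1 to 10.3.3 for one type of case at a time.

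**Step 1: does the list limit severity?** Section 10.3.2 has 8 complete maternal entries (anaemia, hypertension, diabetes, small for gestational age, malpresentation, bleeding/placenta praevia/ruptured membranes, infection, elective birth) and 4 neonatal entries (special care or neonatal unit, jaundice, feeding problems, infection). That makes 8 + 4 = 12. One further maternal entry, on labour complications, is cut off in the text available and is not counted. None of the 12 has a ceiling on severity or a condition on outcome. The centile in the small-for-gestational-age entry defines the condition and does not grade it.

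**Step 2: does any sentence restore reporting?** None in the readable text of 10.3.1 to 10.3.3 says that a listed event goes back to SAE reporting if it also meets criterion a, b or d.

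**Step 3: run cases through both routes.**

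| Case | SAE form and 24-hour report to the CI | Sponsor/REC within 15 days |
|---|---|---|
| Listed admission, serious only through hospitalisation (c) | Exempt, as intended | Not unexpected |
| Admission for hypertension, bleeding/APH or infection that becomes life-threatening (b) or disabling (d) | Exempt: the type is listed | Not unexpected, because the type is listed; must also be related |
| Baby admitted to the neonatal unit in a life-threatening state (b) | Exempt: any such admission is listed | Same |
| Listed admission that ends in death (a) | Ambiguous: exempt if the admission is the event and death its outcome; reportable if the death is itself the event | Same ambiguity; must also be related |

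**Step 4: how much does the list matter on the 15-day route?** Relatedness means arising from a research procedure. Section 6.3 treats both the existing and the new clinic as standard practice and seeks consent only for data collection. On that wording, a hypertensive or infective complication would usually be judged unrelated, so it would miss the Sponsor and REC whatever the list said. The list still has an indirect effect: the 15-day clock starts when the CI becomes aware, and a listed event is never sent to the CI. A related case might therefore never be assessed.

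**Step 5: does the other list widen the gap?** Section 10.3.1 names some conditions as bare diagnoses, postpartum haemorrhage among them, as expected and not reported. Because expectedness turns on whether the type is listed anywhere in the protocol, these also count as expected at any severity on the 15-day route.

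**The case against.** The strongest case against is that the list was plainly written for criterion c. Every complete entry in 10.3.2 is an admission, and death, stillbirth, neonatal death and disability appear in neither list. A sensible site would report a death as an SAE outside the list. Listed events are still recorded, maternal and infant outcomes are collected at birth for every participant (section 7), and the Advisory Board and Sponsor review adverse events before a full trial is designed.

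Much of this stands, and it rules out several stronger readings that a reader might infer:

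- *That deaths are certainly exempt.* The documents do not say so. That result requires treating the admission as the event and the death as its consequence. The definition permits this, since an SAE is an event that "results in death", but reporting the death as an unlisted event is at least as natural.
- *That the SAE list exempts whole diagnoses.* It lists admissions. Bare diagnoses appear only in the 10.3.1 list of expected adverse events.
- *That the list is what keeps these cases from the Sponsor and REC.* Relatedness would stop most of them first.
- *That the decision to go on to a full trial is corrupted.* The key feasibility outcomes are recruitment and retention (sections 7 and 9.1.1), and the safety data are reviewed at the end. What is lost is timeliness during the study.

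The appeal to evident purpose does not settle the life-threatening and disabling cases. There the admission is itself the listed event, and the text exempts it without qualification. A reporting rule should not depend on site staff reading in a limit that is not written.

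**Conclusion.** The point holds as a gap in the reporting rule. A listed admission that is life-threatening or disabling gets no SAE form and no 24-hour report to the CI, and it cannot count as unexpected at any severity. For a listed admission that ends in death, the protocol supports two readings and should choose between them. The main loss is the 24-hour report. With no data monitoring committee, and adverse events reviewed only when the study ends, no other stated step brings prompt review of the individual case.

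All 12 complete entries are affected. The number of cases cannot be calculated, because the protocol gives no rates of severe complications. In a study of about 40-50 women (section 5.3) it is assumed to be small, which limits both the number of missed reports and the burden of restoring them.

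The conclusion assumes that sites apply the wording as written. It also assumes that the unread text, namely the cut-off labour entry and the part of section 10 between 10.1 and 10.3, contains no overriding sentence.

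**What to change.** Three short changes:

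1. In 10.3.2, limit the exemption to listed events that are serious only through hospitalisation or its prolongation (criterion c).
2. In 10.3.2, state that a listed event that also meets criterion a, b or d is reported as an SAE under 10.3.3. This closes the gap for life-threatening and disabling cases and removes the ambiguity over deaths.
3. In 10.3.3, define unexpected as either not listed or more severe than the listed form. The relatedness condition can stay, so this change alone will seldom alter what reaches the Sponsor or REC.

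Routine listed admissions stay exempt. The changes concern reporting only and leave clinical care as it is. The cost is a short protocol amendment and, on the assumption above, a few more SAE forms.
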